Effect sizes ranged from $d=.6$ to $d=1.2$ in directions indicating that opioid blockade reduced post-exercise analgesia, suggesting that EO function partly mediated the effect of acute exercise on pain intensity. The mean effect size across these studies for the impact of EO mechanisms on exercise-related analgesia was $d= .93$ (equivalent to $r=0.42$). This effect size is key to initial analyses of Specific Aim 1. The proposed sample size will result in a power exceeding 0.90 for testing effects of the exercise manipulation on EO function (two-sided $p<.05$ significance criterion). Effect size estimates for the b path in the mediational model reflecting influences of EO function on morphine responses can be derived from our prior work, which indicated an average effect size of $r=0.27$ for associations between natural variations in EO function (opioid blockade effects) and analgesic responses to a single morphine dose across all pain measures and both laboratory evoked pain tasks¹⁸. Effect size for the b path reflecting influences of EO function on chronic back pain intensity can be estimated from Bruehl et al.²⁵, with an effect size of $r=0.26$ for associations between EO analgesic function in the laboratory and diary ratings of chronic back pain intensity (greater EO function was associated with lower daily back pain intensity). Given these effect sizes for the a and b paths in the mediation model, the total sample size for the proposed project was selected as $n=116$, resulting in a power of 0.80 (two-tailed $p<.05$ criterion for significance) for testing mediation effects hypothesized in Aims 1-3 using the proposed bootstrap approach (based on Fritz and MacKinnon⁶⁴).

Data Reduction and Analyses

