Blockade effect variables reflecting EO function will be derived by subtracting evoked pain responses during placebo from comparable responses during opioid blockade (separately for pre-manipulation baseline [BL] and post-manipulation). Given no theoretical rationale for expecting dose response effects with repeated dosing for placebo or naloxone conditions, we will average over the 4 pain stimuli within each of these drug conditions (separately for pre- and post-manipulation sessions) as a means of reducing random measurement error in deriving blockade effects. Blockade effects will be derived such that larger positive values reflect greater EO analgesia. To reduce number of variables, a mean value of the standardized EO function variables (blockade effects) will be derived and will be used initially in analyses (as in Bruehl et al.¹⁸). Chronic pain intensity pre- and post-manipulation will be defined as mean chronic pain ratings during the respective electronic diary sampling periods. As manipulation checks, we will determine whether degree of spontaneous EO function pre-manipulation is correlated significantly with evoked pain sensitivity and chronic pain intensity at BL. Total number of exercise minutes recorded during the post-intervention diary monitoring period (obtained in both groups) will be explored as a potential covariate for use in primary group analyses.

Primary Analyses.

Aim 1: To determine whether an aerobic exercise manipulation increases EO activity in CLBP patients, and whether these EO changes mediate manipulation-induced reductions in evoked pain responsiveness and daily CP intensity. We will conduct Group (exercise, control) x Time (BL, post-manipulation) mixed design ANOVAs to determine whether evoked pain sensitivity and CP intensity decreased significantly in the aerobic exercise group only. We will also conduct Group (exercise, control) x Time (BL, post-manipulation) mixed design ANOVAs on EO function (blockade effect variables pre- and

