post-manipulation) to determine whether EO function increased in the aerobic exercise condition only. We will then test whether group differences in pre- to post-manipulation EO changes mediate group differences in pre- to post-manipulation reductions in evoked pain responsiveness and CP intensity using the bias-corrected bootstrap mediation testing approach of Preacher and Hayes¹⁰⁰. This approach is statistically powerful and not dependent on any assumptions about the sampling distribution of the variables, and was used successfully in our recently published work¹⁸. Per Preacher & Hayes¹⁰⁰, the only precondition for testing mediation will be presence of an effect to be mediated (i.e., the exercise condition is associated with significantly greater reductions in evoked pain responses and CP intensity than the control condition). For any outcomes for which this precondition is met, bootstrap tests of mediation will proceed using the Indirect procedure for SPSS^{100, 101} (<http://www.afhayes.com/spss-sas-and-mplus-macros-and-code.html#sobel>) as in our recent work¹⁸. If the 95% CI for the indirect effect in a given model does not include zero, this will indicate that the hypothesized indirect (mediated) effect is significant at $p < .05$. In this case, a significant indirect path will indicate that the link between aerobic exercise condition and reduced evoked pain responsiveness or CP intensity is significantly mediated by exercise-related EO enhancements. Significant direct and indirect paths jointly for the same outcome will indicate partial mediation. A significant direct path in the absence of a significant indirect path will be interpreted as indicating that the effects of the exercise manipulation on that outcome are mediated via non-opioid mechanisms.

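### A direct path without a significant EO-mediated path will be reported as a non-opioid mechanism, although non-significance at planned power 0.80 does not show that the EO path is absent

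*Combined protocol and SAP*

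**What the plan says.** In section 10.0 (Primary Analyses, Aim 1), mediation by EO change is tested with a bias-corrected bootstrap. The indirect path counts as significant only when its 95% interval excludes zero. The entry condition is a significant group difference on the outcome: "the only precondition for testing mediation will be presence of an effect to be mediated".

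Two patterns then receive a fixed reading. When both paths are significant: "Significant direct and indirect paths jointly for the same outcome will indicate partial mediation". When only the direct path is significant: "A significant direct path in the absence of a significant indirect path will be interpreted as indicating that the effects of the exercise manipulation". The conclusion attached to this second pattern is that the effects "on that outcome are mediated via non-opioid mechanisms".

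The sample-size text in section 10.0 chooses n=116, "resulting in a power of 0.80" for the mediation tests of all three aims. For the exercise-to-EO path alone it says: "The proposed sample size will result in a power exceeding 0.90 for testing effects of the exercise manipulation on EO function". That path also has its own test under Aim 1: "We will also conduct Group (exercise, control) x Time (BL, post-manipulation) mixed design ANOVAs on EO function".

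The plan sets no smallest relevant indirect effect, no equivalence bound and no inconclusive category. The interpretive sentence stands under Aim 1 only. Aim 2 reuses the mediation procedures by cross-reference and Aim 3 follows Aim 2, so its use there is inferred.

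**The concern.** The two parts of the rule carry different weight. A significant direct path is evidence that some of the exercise effect is not carried by the measured EO variable. A non-significant indirect path is only a failure to detect the EO path, and the plan accepts that failure in about one trial in five when the path is real and of planned size. If a real EO path is missed while the direct path is detected, the truth is partial mediation in the plan's own terms, but the report will name a different mechanism. It reaches that conclusion by default, not through a test of any other mechanism.

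Whether exercise works through EO is the second half of each of the three aims, and section 10.0 says the project was powered for exactly these tests. A missed EO path would therefore become a positive statement against the study's central hypothesis. The same report would usually also state that EO function rose significantly with exercise.

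**Working it through.** **Inputs from the documents.** n=116 (section 10.0). Half of the participants go to exercise (section 7.0), so 58 per arm. Exercise-to-EO path d=0.93, r=0.42. EO-to-outcome path r=0.26 for chronic pain intensity and r=0.27 for response to a single morphine dose. Two-sided 0.05.

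**Input assumed.** The direct effect c'. The documents give none, so a range of 0 to 0.30 is shown.

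**Reproducing the plan's figures.**
- d to r: 0.93/√(0.93² + 4) = 0.42, as stated.
- Exercise-to-EO path, 58 per arm, d=0.93: power 0.999, consistent with the stated figure above 0.90.
- Indirect effect, simulated bias-corrected bootstrap with standardised paths: power 0.79 (b=0.26) and 0.80 (b=0.27). The stated 0.80 reproduces. Other scalings give 0.81–0.87.

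The power figure is therefore not in dispute; the question is what a non-significant result may be taken to mean.

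**Model for the label rate.** X=±1; M = aX + error; Y = bM + c'X + error; M and Y are each scaled to variance 1. The indirect effect is ab = 0.42 × 0.26 = 0.109, and the total effect is c' + ab. The label is applied when the total effect is significant (t-test), the direct path is significant (OLS t-test) and the bootstrap interval for ab includes zero. There were 6,000 trials per c', with 1,000 bootstrap draws each; the simulation SE of the label rate is at most 0.5 points.

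| c' (assumed) | Total c' + 0.109 | Share outside EO, c'/(c' + 0.109) | Total and direct both significant | Label applied, all trials | Label as share of previous column |
|---|---|---|---|---|---|
| 0 | 0.109 | 0% | 2.5% | 1.3% | about half, of a rare event |
| 0.15 | 0.259 | 58% | 34.0% | 11.0% | 32% |
| 0.20 | 0.309 | 65% | 54.9% | 14.1% | 26% |
| 0.30 | 0.409 | 73% | 90.0% | 15.4% | 17% |

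The EO path is real in every row. Repeat runs with separate code gave 1.1–1.5%, 11.0–11.5%, 13.0–14.5% and 14.7–15.5% for the label column.

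**Sensitivity.**
- b=0.27: 10.4%, 12.5% and 13.5% at c'=0.15, 0.20 and 0.30.
- Unit error variances instead of unit total variances: 1.1%, 9.1%, 12.9% and 16.3% at c'=0, 0.15, 0.20 and 0.30; repeat runs at 0.15 gave 8.4% and 9.0%. Scaling does matter at c'=0.15.
- A real EO path smaller than planned (c'=0.26, unit error variances): 32%, 49% and 58% at b=0.20, 0.14 and 0.10.

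**What the mislabelled trials look like** (main case, c'=0.15–0.30). The exercise-to-EO test was significant in 99–100% of them. In 84–87% the standardised 95% interval for the indirect effect still contained 0.109, the effect the trial was planned to find.

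**The case against.** **The direct path is real evidence.** This stands. With c' of 0.15–0.30, 58–73% of the true effect lies outside measured EO. A reader might infer that the plan would report the opposite of the truth. The calculations support that only at c'=0, where EO carries everything, and there the label appears in about 1% of trials. Elsewhere the label is incomplete: it leaves out an EO contribution that is present.

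**The size depends on c'.** This stands too. A reader might take 1 − 0.80 and say that one real EO path in five will be mislabelled. The rule also needs significant total and direct effects, so the rate over all trials is lower at the planned paths and small when c' is near zero (2.8% at c'=0.05). The logical fault does not depend on c'.

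**The separate EO test protects.** It does not. It examines only the exercise-to-EO path, and it is significant both when EO mediation is real but missed and when EO rises without driving the outcome.

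**Noise in the EO change score makes matters worse.** This is possible, but the documents give no reliability figure, and the plan averages four stimuli "as a means of reducing random measurement error in deriving blockade effects". No size can be put on it.

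**A formal margin is needed.** A reader might infer this because requiring the interval to exclude 0.109 cuts wrong labels to 1.5–2.3% of all trials. That fall is close to built in, since the true effect was set equal to the margin. With a smaller real path (a=0.42, b=0.12, ab=0.05) the margin rule still allows the claim in 20% of all trials at c'=0.20 and 24–27% at c'=0.30. The correction does not depend on a margin.

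**Conclusion.** The concern holds in limited form. The prespecified sentence draws a conclusion that its own test cannot support: failure to detect the EO path is treated as evidence that the path is absent. At the planned paths this happens despite a real EO path in about 1% of all trials if c' is 0, and in about 11%, 14% and 15% at c'=0.15, 0.20 and 0.30. These figures rest on an assumed c', 1:1 allocation and complete data on 116 participants, and they shift somewhat with scaling.

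The documents do not support saying that the mediation test is underpowered against its stated target, that the trial's conclusion would be reversed, or that the sentence is expressly written for Aims 2 and 3. This should be corrected, because it is a fixed reading of a main result and nothing else in the plan softens it. The tests themselves can stay as they are.

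**What to change.** Replace the sentence under Aim 1 with:

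> A significant direct path without a significant indirect path will be reported as an effect not explained by measured EO change, with EO mediation not demonstrated. The indirect effect will be reported with its 95% bootstrap CI, and a non-opioid mechanism will not be concluded from non-significance alone.

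Add a line saying that the same reading applies to Aims 2 and 3.

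Optional: if the team wants to be able to claim a mainly non-opioid mechanism, it should set a smallest relevant indirect effect for each outcome that the interval must exclude. Scale and sign should be stated, and the value fixed before the group-by-outcome data are analysed. The plan gives no EO-to-outcome path for evoked pain or side effects. Its 0.27 concerns response to a single morphine dose, not the dose needed for 25% relief, so these values need a decision. Such a rule supports mainly, not entirely, non-opioid.

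Cost: a wording change, with no effect on sample size, data collection, tests or the bootstrap interval. The downside is that correct non-opioid results will also be reported as EO mediation not demonstrated. With an optional margin of 0.109 and c'=0.15–0.30, only some would be: 18–26% if EO rises but does not drive the outcome (a=0.42, b=0), and about 5% if exercise does not raise EO (a=0, b=0.26).

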1.0 Background

Chronic pain (CP) affects 100 million individuals in the U.S. CP management has increasingly utilized long-term opioid analgesic therapy, a change associated with increased opioid abuse (via greater exposure in vulnerable individuals), non-pain health consequences (hormone changes, falls), and a dramatic rise in opioid-related overdoses and deaths. Treatment strategies that minimize the need for chronic high-dose opioids are sorely needed. This project will test the novel hypothesis that effective pain relief can be achieved at lower opioid analgesic doses by increasing levels of endogenous opioids (EOs). This hypothesis follows from our prior work demonstrating that analgesic responses to opioid medications are significantly influenced by individual differences in EO activity^{18,19}. Results indicated that for individuals exhibiting higher natural EO levels, morphine produced little incremental analgesic benefit. In contrast, for those displaying less natural EO analgesia, morphine produced significant analgesia. Findings suggested that morphine in effect supplemented lower levels of EO analgesia, making pain responses of individuals lower in EO function who had received morphine look statistically similar to individuals higher in EO function not receiving morphine¹⁸. An Opioid Supplement Model was suggested, in which opioid analgesics supplement EO function, making up the difference necessary to maximize opioid receptor-mediated pain inhibition. Our previous work looked only at natural variations in EO function, and only at a single opioid analgesic dosage. Therefore, the key clinical implication of the Opioid Supplement Model has not been tested: can effective pain relief be achieved at lower opioid analgesic dosages by enhancing EO function? This is one primary aim of the current proposal. While several controlled trials indicate that aerobic exercise is effective for reducing CP intensity, and it is widely assumed these benefits are related to enhanced EO analgesia, this assumption has received surprisingly little empirical testing. Therefore, a second aim of this project is for the first time to directly test whether aerobic exercise training enhances EO function in individuals with chronic low back pain (CLBP), and whether resulting reductions in CP intensity are attributable to these EO changes. Results will provide important information on mechanisms underlying a common CP therapy and have potentially important implications for public health, as results would highlight the potential for strategic combination of lower dose opioid analgesic therapy with nonpharmacological EO-enhancing interventions, potentially reducing negative side effects and mitigating opioid therapy risks.

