The Co-PIs recently reported the first human work directly examining associations between EO function and opioid analgesic responses. Using controlled laboratory methods, associations were examined between spontaneous EO function (indexed by differences in acute pain responses between opioid blockade [naloxone] and placebo conditions) and analgesic responses to morphine, the prototypic mu opioid agonist¹⁸. In a sample of 45 chronic low back pain patients and 31 pain-free healthy controls (combined for analyses given no significant main or interaction effects of subject type), significant associations were observed between EO function and morphine analgesic responses on all 7 measures of pain responsiveness examined across two different evoked pain tasks (ischemic pain, thermal pain)¹⁸. We recently extended these findings to clinical chronic pain¹⁹. Individuals exhibiting less EO inhibition of their chronic back pain (less effect of opioid blockade on back pain intensity) experienced greater relief of their back pain with morphine administration relative to higher EO individuals¹⁹. To isolate the source of the effects noted in Bruehl et al.¹⁸ and provide a clear means of portraying them, median splits were conducted on EO function variables derived for each pain measure, with placebo condition and morphine condition responses for each measure then compared across the resulting groups. The pattern of results indicated an intriguing source of these observed associations. First, as expected, when EO systems were intact (placebo condition), individuals exhibiting relatively lower spontaneous EO activity were significantly more responsive to both evoked pain tasks on all measures. Second, individuals with lower EO function exhibited substantial morphine analgesic responses whereas those with higher EO function did not.

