Post-Manipulation 5 day Electronic Diary Monitoring Period (\approx Week 11, between Lab Visits 4-5): Identical to pre-manipulation electronic diary procedures described above.

Description of Laboratory Visit Procedures:

All laboratory procedures will be conducted with participants seated upright in a comfortable chair. Each participant's series of three laboratory sessions (placebo, naloxone, morphine) carried out both pre- and post-manipulation will be scheduled within an ≈ 10 day period, at the same time of day to control for variance due to circadian rhythms.

Study Drug Protocol: Study drugs will be administered (in double-blind fashion) in randomized, counter-balanced order. The assigned study drug will be administered within a given session over 4 infusions (2 min each) according to the following protocol, depending on the assigned drug for that visit: 1) 4 doses of saline placebo (20ml each), 2) an 8mg dose of naloxone (in 20ml saline vehicle), followed by saline, 4mg naloxone, and saline, or 3) morphine sulfate (0.03 mg/kg in 20ml saline vehicle initially, followed by 3 incremental doses of 0.02mg/kg each). To avoid excessive morphine doses (and increased side effect risks) for individuals who are obese, a modified weight adjustment will be employed for individuals more than 30% over ideal body weight based on subjects' observed weight in clinic compared to appropriate ideal body weight for males (50kg+2.3kg for each inch over 5 feet) or females (45.5kg +2.3kg for each inch over 5 feet) [from <http://www.globalrph.com/>]. For individuals meeting this obesity criterion, morphine dosage will be based on Adjusted Body Weight rather than actual body weight, as calculated by: $\text{Ideal Body Weight} + 0.4 (\text{actual weight} - \text{Ideal Body Weight})$.

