The other study drug, morphine, is an FDA-approved opioid analgesic with a very long history of use in standard clinical practice. It can produce dose-dependent side effects including sedation, somnolence, nausea, brief vomiting, euphoria, and respiratory depression. The cumulative dose to be used in the proposed study (0.09 mg/kg) will be weight adjusted, and represents a relatively low dose within the normal range of dosages used in standard clinical practice, representing a dosage only slightly larger than in our recent work (0.08 mg/kg; Bruehl et al., 2013). This should help limit any negative side effects. The half-life of morphine is approximately 2 hours, and study participants will be kept under observation in each study session until any side effects remit to the point where it is safe for them to leave unassisted. If morphine side effects are severe, these effects will be immediately reversed by administration of naloxone as determined appropriate by the study physician.

As part of this study, half of the participants will be randomly assigned to undergo a 6-week supervised aerobic exercise manipulation as described above. To maximize safety with this type of exercise, individuals with a history of cardiovascular disease are excluded from participating in this study. The intensity of this aerobic exercise training will start low but progressively increase over the 6-week intervention period. Safety and possible discomfort associated with these increases in exercise intensity will be minimized via close monitoring by a certified personal trainer of participant's heart rate, perceived exertion levels, and back pain intensity during exercise. Exercise intensity will be adjusted as appropriate to maximize the participant's level of conditioning while minimizing exacerbation of back pain. In addition, participants will be able to choose your preferred form of exercise from several available options.

In the event new information becomes available that may affect the risks or benefits associated with this study, participants will be notified so that they can make an informed decision whether or not to continue their participation in this study. There may be unknown or unanticipated adverse effects in addition to those listed.

8.0 Reporting of Adverse Events or Unanticipated Problems Involving Risk to Participants or Others

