Aim 2: To determine whether the exercise manipulation is related to achieving analgesic targets at lower opioid analgesic dosages, and whether these changes in analgesic requirements are mediated by pre-post EO changes. We will calculate dose response curves (per Prentice¹⁰²) based on morphine condition evoked pain responses at the four incremental morphine dose levels (separately for pre- and post-manipulation). Based on results of our prior work¹⁸, a 25% reduction in pain sensitivity relative to pre-exercise placebo pain responses will be the target. The total dosage of morphine needed at pre-manipulation BL to achieve a 25% reduction in pain responses (based on the dose response curve) will be compared to the dose of morphine needed to achieve a 25% pain reduction at post-exercise. We will conduct Group (exercise, control) x Time (BL, post-manipulation) mixed design ANOVAs to determine whether the total morphine dose required to achieve 25% pain relief decreased significantly in the exercise group only. We will then use mediation analysis procedures as described above to test whether group differences in pre- to post-manipulation EO changes mediate group differences in pre- to post-manipulation reductions in morphine dosage required to achieve 25% relief. The only precondition for conducting these mediation tests will be that there is an effect to be mediated, i.e., the exercise manipulation significantly alters the morphine dosage required to achieve 25% pain relief.

Aim 3: To determine whether the exercise manipulation is related to achieving a 25% morphine-induced reduction in evoked pain responsiveness with fewer negative side effects and abuse-relevant effects, and whether these changes are mediated by pre- to post-manipulation EO changes. Aim 3 analyses will parallel Aim 2 except that side effects and abuse-relevant effects at the 25% pain reduction target will be the DV.

Secondary Analyses.

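### The Aim 2 endpoint, the morphine dose for a 25% reduction, has no rule for participants whose curve misses the target, meets it without morphine, or is flat or reversed

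*Combined protocol and SAP*

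**What the plan says.** - **Doses** (6.0 Study Procedures, Study Drug Protocol): "morphine sulfate (0.03 mg/kg in 20ml saline vehicle initially, followed by 3 incremental doses of 0.02mg/kg each".
- **Target** (10.0, Aim 2): dose-response curves are calculated from evoked pain responses at the four morphine levels, separately before and after the manipulation, and "a 25% reduction in pain sensitivity relative to pre-exercise placebo pain responses will be the target". The baseline anchor therefore applies at both time points.
- **Test** (10.0, Aim 2): a Group x Time mixed ANOVA is run "to determine whether the total morphine dose required to achieve 25% pain relief decreased significantly in the exercise group only".
- **Mediation** (10.0, Aim 2): "The only precondition for conducting these mediation tests will be that there is an effect to be mediated", that is, a significant effect of exercise on the required dose.
- **Aim 3** (10.0): the analysis parallels Aim 2, except that "side effects and abuse-relevant effects at the 25% pain reduction target will be the DV".
- **Power** (10.0): n=116 is stated to give 0.80 for the mediation tests of Aims 1–3.
- **Measures** (6.0, Thermal Pain Task Procedures): heat threshold, heat tolerance and an MPQ rating are collected after each dose. Aim 2 does not say which of them carries the 25%.

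**The concern.** The ANOVA and the mediation model both need one number per participant per period. There are three ways in which the curve may not supply one:

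1. The curve does not reach 25% by 0.09 mg/kg.
2. The target is already met without morphine at post-test. This can happen because it stays tied to pre-exercise placebo.
3. The fitted slope is flat or reversed, so the solved dose means nothing.

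In cases 1 and 2 there is no value within the studied range. I found no rule on extrapolation, censoring, exclusion or imputation. The averaging described under Data Reduction concerns blockade effects, not the morphine dose.

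The plan's own background makes these cases foreseeable. Section 1.0 reports that "for individuals exhibiting higher natural EO levels, morphine produced little incremental analgesic benefit", and section 3.0 that "individuals with lower EO function exhibited substantial morphine analgesic responses whereas those with higher EO function did not". Section 7.0 describes the top dose as "representing a dosage only slightly larger than in our recent work (0.08 mg/kg" in that earlier work.

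Without a rule, the analyst must choose after seeing the data. Using the fitted value as written lets a few near-flat curves produce extreme doses that dominate the ANOVA. Dropping cases selects on morphine response and, at post-test, possibly on the exercise effect itself. It also reduces the n=116 behind the stated power for Aims 2 and 3. Because the Aim 2 mediation test runs only after a significant dose effect, its chance of success cannot exceed the power of the dose test.

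**Working it through.** **Figures from the plan**

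- Top cumulative dose: 0.03 + 3 × 0.02 = 0.09 mg/kg, as stated in 7.0.
- a path: r = d/√(d²+4) = 0.93/√(0.93²+4) = 0.42, as stated.
- Mediation power, bias-corrected bootstrap, n=116, a=0.42: simulated 0.80–0.83 with b=0.27 and 0.78–0.81 with b=0.26. The plan's 0.80 reproduces, provided that every participant supplies a dose.
- Same simulation with fewer evaluable participants (b=0.27): 0.71–0.76 at 93, 0.65–0.72 at 81, 0.50–0.56 at 58.

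**How often the target could be missed (assumed values)**

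If the true percent reduction at 0.09 mg/kg is normal with mean m and SD s, then P(miss) = Φ((25 − m)/s).

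- m=25: Φ(0) = 50%.
- m=35: s=10 gives Φ(−1) = 16%; s=30 gives Φ(−0.33) = 37%.
- m=45: s=10 gives Φ(−2) = 2%; s=30 gives Φ(−0.67) = 25%.

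With straight-line fits to four doses (m 25–45%, s 10–20, residual SD 5–10 points), 0.1–19% of curves have a zero or reversed slope. The unbounded solved dose has a simulated SD from 0.2 to over 100 mg/kg, against a top dose of 0.09.

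**Consequence of each handling rule (assumed values)**

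Inputs: 58 per arm; between-person SD 15 in the reduction at 0.09; exercise adds 8 points at post-test; BL-to-post slope correlation 0.7; post-test intercept SD 10; post-test placebo error SD 5; straight-line fits; 1,500 replicates. Power of the dose test at reading noise SD 10:

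| Mean reduction at 0.09 | Extrapolated | Dropped if outside 0–0.09 (share lost) | Bounded score, BL covariate |
|---|---|---|---|
| 20% | 0.02 | 0.14 (78%) | 0.70 |
| 25% | 0.03 | 0.19 (69%) | 0.76 |
| 30% | 0.03 | 0.26 (60%) | 0.79 |
| 40% | 0.05 | 0.37 (40%) | 0.84 |
| 50% | 0.12 | 0.46 (26%) | 0.82 |

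- Noise SD 5: 0.03–0.42 extrapolated, 0.19–0.72 dropped (15–75% lost), 0.78–0.89 bounded.
- Recoding the same assumptions independently agrees to within about 0.04. If cases outside 0.03–0.09 are dropped instead, power is 0.09–0.26.
- Type I error of the bounded ANCOVA: 0.047–0.056.
- Same bounded score tested as change, which with two time points is the planned Group x Time test: 0.65–0.73 (noise 10) and 0.76–0.82 (noise 5).
- Selection, noise 10: retained participants have a true baseline reduction 10–19 points larger than those dropped. Their EO level is 0.18–0.34 SD lower if r=0.27 holds at this level. This describes EO level, not EO change, which is the mediator.

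**Sensitivity**

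- Exercise effect 5 points: bounded-ANCOVA power falls to about 0.4–0.5 and stays ahead of the alternatives.
- Logit curve in log dose, means 20/30/50, noise 10: extrapolated 0.21/0.10/0.07, dropped 0.23/0.33/0.61, bounded 0.76/0.82/0.85. At mean 50, noise 5: 0.25, 0.79 and 0.91.
- Exercise also flattens the morphine curve, so that the response at 0.09 is unchanged: bounded 0.17–0.30, dropped 0.07–0.14, extrapolated 0.02–0.03.

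**Scale of the 25%**

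For an assumed 44 °C threshold, 25% of the Celsius value means 1.25 × 44 = 55 °C. A quarter of the rise above the 32 °C start means 32 + 1.25 × 12 = 47 °C.

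**The case against.** The strongest reply is that the size of the problem is unknown. The plan bases its 25% target on prior work that is not reproduced here. The evidence for weak responders is a group-level median split pooling 45 patients with 31 pain-free controls. An r of 0.27 is about 7% of variance (0.27² = 0.073), so EO level says little about which individuals will miss the target. The 8-point effect has no source in the documents, and the simulated curves are not the generalised probit/logit method that the plan cites. Unlimited straight-line extrapolation is also an extreme comparator. All of this stands, and it removes any claim to a forecast of power or loss. It does not supply the missing rule, and the ordering of the methods survived every variation tried.

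A second reply is that the Group x Time ANOVA is not itself at fault. That is right: a bounded score can be used in it, and the baseline covariate is a separate gain in efficiency.

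A third is that the unnamed measure and the mediation precondition are separate matters. The precondition exists regardless of missing doses. The plural ANOVAs may mean one per measure, and pain relief reads more naturally as a rating than as a temperature. The measure is therefore a secondary point, but a percentage target cannot be computed until it is settled.

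A reader might infer that the stated 0.80 power is wrong, or that most participants will have no usable dose. The documents support neither. The 0.80 reproduces on its own inputs, and no attainment rate is given.

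**Conclusion.** The concern holds as a gap in the definition of a primary-analysis variable. The Aim 2 dose has no value within the studied range, or no meaningful value, for a foreseeable group of participants, and Aim 3 inherits this. Aim 1 is unaffected. It is more than missing detail, because the two default readings, taking the fitted value as it falls or dropping the case, did worse than a bounded score in every scenario simulated.

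All the powers and loss rates are illustrations on assumed means, SDs, noise, effect size and curve shape; the cited curve method was not simulated. Only the advantage of the bounded score over extrapolating or dropping is robust. It would be wrong to conclude that the fix secures power near 0.8. Power is about 0.4–0.5 with a 5-point effect, and low under any method if exercise flattens the morphine curve, which is one reading of the plan's own supplement model.

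**What to change.** Before outcome data by arm are examined, amend the Aim 2 and Aim 3 text in 10.0:

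1. No dose is extrapolated beyond the studied range, and no participant is dropped for being out of range.
2. For analysis only, score each period in this order:
   - 0 if the post-test placebo session already meets the target;
   - for a flat or reversed curve, 0.09 flagged as not reached, unless the fitted response meets the target at all four doses, in which case 0.03;
   - 0.03 if the fitted curve meets the target at the lowest dose;
   - the fitted dose if it lies between 0.03 and 0.09;
   - otherwise 0.09, flagged as not reached.
3. Make the primary test an ANCOVA of the post-test score on group with the baseline score as covariate. Add a rank or censored model as sensitivity analysis, and use the same score in the mediation model.
4. Name the evoked-pain measure that carries the 25% and, if it is a temperature, its scale origin. The choice is the trial team's.
5. For Aim 3, report by arm the share within, above and below range. State which side-effect value is assigned to out-of-range participants, and that values assigned to non-reachers are not at equal analgesia.

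The cost is SAP wording and modest programming. No new data are needed, since pain and side effects are recorded after every dose and each period has a placebo session. The price is that the result becomes a shift in a bounded dose, and values at the limits hide differences beyond them.
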